2.1. OBJECTIVES

2.1.1. PRIMARY OBJECTIVE:

• To estimate the overall, age and gender specific prevalence of HPV in the oropharynx in patients undergoing tonsillectomy for non-malignant conditions

2.1.2. SECONDARY OBJECTIVES:

- To compare the HPV oropharynx prevalence between different sites—in order to identify the different reservoirs of HPV infection
- To describe the distribution of HPV seropositivity in the study population by age and gender
- To describe HPV-type distribution overall by age, gender, and sampling site
- To describe distribution by age and gender of patients who are both HPV PCR positive and anti-HPV L1 sero-positive – predicting persistent HPV infection
- To provide preliminary estimates of the clearance and persistence of HPV infection and antibodies in the oropharynx, as detected in follow-up oral fluid, finger tips/nail brushings and urine samples
- To assess the presence of anti-L1 HPV antibodies in saliva as a marker of vaccination or previous infection in the oral cavity
- To assess the presence of HPV in the urine
- To assess the presence of HPV in finger tips/nail brushings
- To provide preliminary evaluation of the performance of potential non-invasive tests for the detection of HPV infection in the mouth against HPV detection rates in tonsillectomy and oropharyngeal scrapes
- To identify the change in overall prevalence and distribution of HPV in tonsils over time, and to describe preliminary data on age and gender specific changes over time
- To provide preliminary data on the potential effect of HPV vaccination in the prevention of oral infection

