7.4. SAMPLE ANALYSIS

All samples will be analysed using laboratory manuals and standard operating procedures applicable to that organisation.

Table 3: List of laboratories analysing samples

Testing Laboratory	Sample
DDL Diagnostic Laboratory Diagnostic Service Unit [name] The Netherlands	Fresh TonsilsArchive TonsilsOral rinse
Universiteit van Antwerpen Vaxinfectio – CEV [name] [name] Belgium	• Urine
CEVAC Center For Vaccinology UZ GENT - 1BA [name] Belgique	• Serum
InHANSE Laboratory CRC Building School of Cancer Sciences, 3rd Floor, University of Birmingham [name], UK	Nail BrushingsWhite Blood CellsSerum

Testing Laboratory	Sample
GlaxoSmithKline Vaccines Clinical Immunology R & D Department/Building 7 [name] [name] – Belgium	 Oral Mucosal Transudate Urine Fresh Tonsils Archive Tonsils Oropharyngeal brushings

- The oral fluid, nail brushings, oropharyngeal scrapes and urine samples will be tested for HPV DNA by PCR. We may also test them for HPV viral load, viral RNA and p16 RNA. They may also undergo other detection methods, such as in-situ hybridisation (ISH). The oral fluid may also be tested for anti HPV L1 antibodies. Other antibodies e.g. anti E6/7, nucleic acids, other HPV related proteins and total antibodies may also be assayed.
- 2. The tonsil samples will be tested for HPV DNA by PCR. They may also undergo other forms of detection of HPV such as in-situ hybridisation and other tests that may be developed in future for HPV detection. The tonsil samples will also be examined histologically for pre-malignancy to examine the molecular profile and genetic changes within the pre-malignant sample and to compare it to those of the normal tonsil, using immunohistochemical, DNA, mRNA and proteomics techniques.
- 3. The blood samples will be tested for antibodies to the HPV L1, and other HPV antibodies. Also other protein testing may be performed. Samples may undergo other forms of detection for HPV within the blood, such as HPV nucleic acids and HPV virus particles.

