The rate of HPV persistence will be calculated as the proportion of baseline HPV-positive patients who again test HPV-positive in oral fluid, fingertip/nail brushings and urine samples collected after approximately 3 - 6 months. The rate of oral HPV infection clearance will be calculated as the proportion of baseline HPV-positive patients who test HPV-negative in oral fluid, fingertip/nail brushings and urine samples collected after approximately 3 - 6 months.

HPV incidence will be calculated as the proportion of baseline HPV-negative patients who test HPV positive in oral fluid, fingertip/nail brushings and urine samples collected after approximately 3 - 6 months. Exact 95% confidence intervals will be computed.

Multi variable regression models will be used to calculate the odds ratios of different risk factors for having HPV DNA in the tonsil and in the oropharynx, Variables to be included in the model (e.g. serological markers and clinical risk factors such as HPV vaccination status, tobacco and alcohol use) will be selected on the basis of descriptive statistics/possible causal relationship and/or a stepwise approach. Analysis of results may be performed to identify a possible marker or combination of markers for screening for persistent HPV infections in the oropharynx.

Among females in the target age class for vaccination (12 to 24 years), exploratory analyses will compare the HPV prevalence rate in HPV vaccinated and non HPV vaccinated patients using a Fisher's exact test. Association between HPV vaccine and oral HPV infection will be assessed using a case-control approach. Cases will be patients with HPV positive oral sample and controls will be patients with HPV negative oral sample. The exposure to vaccine will be compared between the case and the control groups using logistic regression, OR and its 95% confidence interval will be derived.

Prevalence of HPV in tonsils will be described and compared between the current cohort and the comparison historical cohort using a Cochran-Mantel-Haenszel test with stratification by age group and gender.

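### The risk-factor model in Section 12.2.2 may contain both antibody status and HPV vaccination, which would bias the vaccination odds ratio towards protection if infected patients are more often seropositive

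*Protocol*

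**What the plan says.** Protocol Section 12.2.2 describes the model, which covers two sites, tonsil and oropharynx (the quotation stops before the second is named): "Multi variable regression models will be used to calculate the odds ratios of different risk factors for having HPV DNA in the tonsil and in" … Its candidates are given as "Variables to be included in the model (e.g. serological markers and clinical risk factors such as HPV vaccination status, tobacco and alcohol use", and they "will be selected on the basis of descriptive statistics/possible causal relationship and/or a stepwise approach". No rule keeps antibody and vaccination status out of the same model.

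The next sentence has a different, predictive aim: "Analysis of results may be performed to identify a possible marker or combination of markers for screening for persistent HPV infections in the oropharynx". The text does not say whether this uses the same models.

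On what antibody represents, Section 2.1.2 has the objective "To assess the presence of anti-L1 HPV antibodies in saliva as a marker of vaccination or previous infection in the oral cavity". On what is measured in serum, Section 7.4 says "The blood samples will be tested for antibodies to the HPV L1, and other HPV antibodies". Section 12.2.2 does not say which of these count as serological markers.

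The vaccine question also has its own analyses, in the following paragraph of Section 12.2.2. Among females aged 12 to 24, "exploratory analyses will compare the HPV prevalence rate in HPV vaccinated and non HPV vaccinated patients using a Fisher's exact test". A case-control analysis, which also reports a vaccine odds ratio, follows: "The exposure to vaccine will be compared between the case and the control groups using logistic regression, OR and its 95% confidence interval will be" … Neither mentions antibody.

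**The concern.** An odds ratio offered as that of a risk factor should not be adjusted for a consequence of both the exposure and the outcome. On the protocol's own account, anti-L1 antibody can arise from vaccination or from infection. Within the seropositive stratum, vaccinees are there mainly because they were vaccinated, while unvaccinated patients are there partly because they were infected. The unvaccinated comparison group is then enriched for HPV-positive patients, and vaccination looks protective even if it does nothing. A larger sample narrows the interval around the wrong value.

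The selection rule adds to the risk. The stronger the link between antibody and infection, the larger the bias, and the more likely a stepwise procedure is to keep antibody. The model would then report a multivariable-adjusted vaccination odds ratio. Readers might prefer it to the simpler dedicated analyses, in a study that lists preliminary data on vaccine effect among its objectives.

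**Working it through.** The protocol states no figure for this model, so there is nothing to reproduce. The check asks what the model would report for a vaccine with no effect.

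**Inputs from the protocol.** 925 patients (Section 12.3). 150 vaccinated, the number of vaccinated women assumed in Section 12.4, so 150/925 = 16.2%. HPV prevalence 6.5% (Section 12.3), with 2% and 10% also tried.

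**Assumptions not in the protocol, shown as ranges.** s = probability that vaccination makes a patient seropositive, 30% to 98%. a = seropositivity in unvaccinated HPV-negative patients, 5% to 10%. b = seropositivity in unvaccinated HPV-positive patients, 10% to 50%.

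**Model.** V = vaccinated, D = HPV DNA positive, S = seropositive. V and D are independent, so the true vaccination odds ratio is 1. Vaccination and infection act independently on antibody: P(S | V=1, D) = 1 − (1 − base)(1 − s), where base = a if D=0 and b if D=1. For unvaccinated patients P(S) = base. Logistic models for D were fitted to expected cell counts, with and without S.

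**One case by hand (s = 95%, a = 10%, b = 30%, prevalence 6.5%).**

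| Group | HPV+ | HPV− | HPV+ and seropositive | HPV− and seropositive |
|---|---|---|---|---|
| Unvaccinated (775) | 50.4 | 724.6 | 50.4 × 0.30 = 15.1 | 724.6 × 0.10 = 72.5 |
| Vaccinated (150) | 9.75 | 140.25 | 9.75 × 0.965 = 9.41 | 140.25 × 0.955 = 133.9 |

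- Without antibody: (9.75/140.25) / (50.4/724.6) = 1.00.
- Among seropositives: (9.41/133.9) / (15.1/72.5) = 0.34. In general this is P(S|1,1)P(S|0,0) / [P(S|1,0)P(S|0,1)], with arguments in the order V, D. It is close to a/b when nearly all vaccinees are seropositive.
- Main-effects model with V and S: 0.35.

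**Expected adjusted vaccination odds ratio (95% CI), true value 1, prevalence 6.5%.** Columns give b v a.

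| s | 15% v 10% | 20% v 10% | 30% v 10% | 50% v 10% | 50% v 5% |
|---|---|---|---|---|---|
| 95% | 0.69 (0.26–1.82) | 0.52 (0.21–1.30) | 0.35 (0.15–0.82) | 0.21 (0.10–0.46) | 0.11 (0.05–0.24) |
| 50% | 0.84 (0.38–1.86) | 0.72 (0.33–1.59) | 0.55 (0.25–1.21) | 0.36 (0.17–0.79) | 0.21 (0.09–0.47) |
| 30% | 0.90 (0.43–1.89) | 0.81 (0.38–1.71) | 0.67 (0.32–1.43) | 0.49 (0.23–1.06) | 0.32 (0.14–0.71) |

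When b = a the adjusted odds ratio is 1.00. With antibody left out it is 1.00 in every scenario. With 98% of vaccinees seropositive, it is 0.51 at 20% v 10%, 0.26 at 40% v 10% and 0.10 at 50% v 5%. Moving prevalence from 2% to 10% changes the odds ratio only from 0.350 to 0.352 (s = 95%, 30% v 10%), so prevalence affects precision and hardly the bias.

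**Selection.** Backward elimination at 0.05 was simulated with a null vaccine and 98% of vaccinees seropositive. Prevalence was 3.1% (the pooled tonsil rate in Table 2, 30/978) or 6.5%. Both terms stayed in about 66% and 92% of studies at 40% v 10%, in 98% to 100% at 50% v 5%, and in roughly 13% to 25% at 20% v 10%.

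**The case against.** The strongest reply is that the protocol does not commit to this model. The variables are examples, selection follows, and one permitted criterion is a possible causal relationship, which a careful analyst would use to exclude antibody. Section 12.2 defers detail to a statistical analysis plan that is not shown. A reader might infer that the plan fixes antibody as a covariate and that its odds ratios are therefore biased as specified. The documents do not support that: joint entry is allowed and invited, not required. The point still stands, because the protocol names the variable itself, and its and/or wording lets the stepwise route be used alone.

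A second reply is that the size is assumed. This is correct. A reader might infer that an ineffective vaccine would necessarily look strongly protective. At a 1.5-fold or 2-fold contrast in seropositivity every interval in the table includes 1, and with no contrast there is no bias. The objective cited speaks of previous infection and of antibody in saliva, whereas the outcome is HPV DNA now and the serological markers are undefined. The argument applies to antibodies that vaccination raises, such as anti-L1, and only so far as they track current HPV DNA.

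Third, the vaccine question has its own Fisher's exact test and case-control regression with no stated antibody term, and no listed objective is a risk-factor analysis. This limits the consequence but does not remove it, since the model would still report a vaccination odds ratio.

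Finally, serology is a legitimate predictor in the marker search. That is a reason to separate the two aims, not to drop serology.

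**Conclusion.** The point holds in conditional form. Section 12.2.2 permits antibody status and vaccination in one risk-factor model under a selection rule that can bring both in. If it does, and infected patients are more often seropositive, the vaccination odds ratio is biased towards protection. For a null vaccine the expected value is about 0.1 to 0.9 over the ranges tried, and 1.0 if antibody is unrelated to current HPV DNA or is omitted. The direction rests on infection raising seropositivity and on vaccination and infection acting independently on antibody. The size rests on seropositivity figures that the protocol does not give.

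The effect is confined to this supporting secondary model. The primary prevalence estimate is untouched, and so are the dedicated vaccine analyses as written. Behavioural odds ratios could also be distorted, because antibody may lie downstream of exposure through infection. That was not quantified here. The change is worth making because it is cheap and removes the risk of two conflicting vaccine odds ratios.

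**What to change.** Add a sentence to Section 12.2.2, carried into the statistical analysis plan: antibodies raised by vaccination, such as anti-L1, are not candidate variables in any model whose vaccination or behavioural odds ratios are interpreted, and stepwise selection may not add them. State separately that serological markers belong to the marker and screening analysis, which is done by vaccination status, and that their odds ratios there are predictive and not those of risk factors. Say which antibodies are meant by serological markers. The cost is a short text change. No new data or samples are needed.

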Secondary Objectives	 To compare the HPV oropharynx prevalence between different sites—in order to identify the different reservoirs of HPV infection To describe the distribution of HPV seropositivity in the study population by age and gender To describe HPV-type distribution overall by age, gender, and sampling site To describe distribution by age and gender of patients who are both HPV PCR positive and anti-HPV L1 sero-positive – predicting persistent HPV infection To provide preliminary estimates of the clearance and persistence of HPV infection and antibodies in the oropharynx, as detected in follow-up oral fluid, finger tips/nail brushings and urine samples To assess the presence of anti-L1 HPV antibodies in saliva as a marker of vaccination or previous infection in the oral cavity To assess the presence of HPV in the urine To assess the presence of HPV in finger tips/nail brushings To provide preliminary evaluation of the performance of potential non-invasive tests for the detection of HPV infection in the mouth against HPV detection rates in tonsillectomy and oropharyngeal scrapes To identify the change in overall prevalence and distribution of HPV in tonsils over time, and to describe preliminary data on age and gender specific changes over time To provide preliminary data on the potential effect of HPV vaccination in the prevention of oral infection
Duration	6 months setup and pilot, recruitment over 36 months and 12 months for analysis
Population	Prospective cohort of up to 1000 eligible patients (minimum set of samples) undergoing tonsillectomy and a historical comparison group of 1250 patients who underwent tonsillectomy in early 2000's
Eligibility	 Inclusion criteria for prospective cohort: The following patients are eligible: Patients undergoing tonsillectomy for non-cancer reasons including operations for: recurrent tonsillitis, snoring surgery or obstructive sleep apnoea Age 0 to 65 years Patient or parent(s)/legal guardian(s) has given written informed consent/assent

	Exclusion criteria:
Eligibility	The following patients are not eligible to join the study: Patients undergoing adenoidectomy alone with no tonsillectomy Patients with previous oropharyngeal cancer or oral cancer, or any other head and neck cancer such as nasopharyngeal or laryngeal cancer that is currently undergoing or previously has been diagnosed or treated Learning disability preventing an adult over 16 years old from giving their own consent

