7. STUDY PROCEDURES AND SAMPLE COLLECTION

All samples should be collected in accordance to the study procedure manual developed by GSK with details of sample collection kits, volume of samples to be collected and storage temperature requirements.

For a patient to be eligible for inclusion in the data analysis, the following samples are a minimum requirement:

- Oral samples
- Blood
- Oropharyngeal brushings
- Tonsils

 After written consent is obtained, the patients (above 16 years old only) will complete a short study questionnaire including age, gender, history of tobacco/alcohol use, sexual history including age of start of sexual intercourse, lifetime numbers of sexual partners, engagement in oral sex and lifetime number of oral sex partners etc.

- 2. An HPV vaccination history will also be taken. Consent/assent will also be taken from the patient, parent(s) or their guardian(s), if applicable, to obtain the patient's HPV vaccination status from vaccine and medical health records from their GP and/or other relevant health and educational authorities. The data requested will include confirmation of HPV vaccination status, including dates, number of doses and the type of vaccine given.
- 3. Oral fluid samples will be collected for HPV PCR and HPV antibody tests, using an oral rinse and an exudate collection device respectively.
- 4. A 20 30 ml urine sample will be collected for HPV PCR test.
- 5. Blood serum will be taken for HPV and biomarker serology tests. This can be taken after the patient has been anaesthetised if necessary. 20 mls of blood will be taken from patients aged 16 years and above, 10 mls from patients below 16 years old.
- 6. Once the patient is anaesthetised, two brush cytology scrapings using cytobrushes (provided) will be taken: one from the posterior pharynx including above and below the soft palate so that the adenoidal area is included, and a second separate brush scrape will be taken from the back of the tongue (base of tongue).
- 7. Tonsillectomy will then be performed and the tonsillar tissue will be placed in 10% buffered formalin and sent to the pathology department for paraffin embedding according to a specific protocol.
- 8. Stratified sampling will be employed to ensure that sufficient numbers of patients are recruited from all age groups, especially the age groups between 10 and 20 years old.

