12.3. SAMPLE SIZE CONSIDERATIONS

An analysis of current literature suggests that in a population recruited between 1990 and 2000, the prevalence of oral HPV was about 6.5%, varying from 0% - 10%. However, in an analysis of oropharyngeal scrapes and oral washings, the prevalence of HPV detection was much higher at 31%.

Pilot data of patients having tonsillectomy at University Hospital Coventry over two 3-month time periods are shown below in table 3. The number of tonsillectomy operations performed at the Heart of England NHS Foundation Trust - is approximately 50% of that for University Hospital Coventry quoted below.

Table 5: The number of tonsillectomy operations performed at University Hospital Coventry.

Age Group*	Number of Monthly recruitment (%)		
0-4	7 (12%)		
5-9	12 (20%)		
10-14	7 (12%)		
15-19	10 (17%)		
20-24	6 (10%)		
25-29	5 (8%		
30-34	4 (7%)		
35-39	5 (8%)		
40-44	1 (2%)		
45-49	1 (2%)		
50-69	1 (2%)		
Total	59		

^{*}There was an equal distribution of males and females in the group.

We plan to enrol 925 patients. The precision of the overall prevalence estimate that would be achieved with such a number is summarised in Figure 1 for prevalence ranging from 1 to 31 %. For example, if the observed prevalence is 10 %, the 95 % confidence interval for the overall population will be 8.4 to 11.8 % corresponding to a relative precision of 17 %.

[figure not shown]

Figure 1: Precision (95% confidence interval) of the prevalence estimate versus the prevalence observed in a random sample of 1250 patients.

We will also undertake a stratified sampling strategy to allow comparisons between those aged 14 and under (non-exposed, approximately one third of the cohort), and patients over 14 years of age (exposed) to allow the determination of the age of acquisition of infection and the optimal age of start of vaccination. The stratified sampling strategy will recruit patient subgroups as follows:

Table 6: The stratified sampling strategy for patient recruitment.

Age group	Sample size (%)		
0-4	150 (16.5%)		
5-9	150 (16.5%)		
10-14	150 (16.5%)		
15-19	150 (16.5%)		
20-24	150 (16.5%)		
25-34	100 (11%)		
35-44	60 (5.5%)		
45-65	15 (1.0%)		
Total	925		

[figure not shown]

Figure 2: Precision (95% confidence interval) of the prevalence estimate versus the prevalence observed in a random sample of 100, 150, and 250 patients.

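### Risk-factor models in section 12.2.2 allow data-driven variable selection with few expected tonsil events, and name questionnaire variables collected only from about age 16 without declaring that population

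*Protocol*

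**What the plan says.** Section 12.2.2 plans multivariable models giving odds ratios for "different risk factors for having HPV DNA in the tonsil and in the oropharynx". The candidates are given as examples: "serological markers and clinical risk factors such as HPV vaccination status, tobacco and alcohol use". They "will be selected on the basis of descriptive statistics/possible causal relationship and/or a stepwise approach". No number of variables is stated, no link to the number of events is made, and no analysis population is named. The same paragraph adds that the results may be used to look for markers for screening for persistent infection.

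Tobacco, alcohol and sexual history come from the questionnaire in section 7, item 1, where "the patients (above 16 years old only) will complete a short study questionnaire". The Study Summary sets the limit at 16 or over, so the two places differ by one year of age. Section 7 puts no age limit on vaccination history or on blood for serology.

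On size, section 12.3 states "We plan to enrol 925 patients", while the Study Summary has "Prospective cohort of up to 1000 eligible patients". Section 12.2 leaves analysis detail to a SAP that is not shown.

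**The concern.** Two of the routes allowed, descriptive statistics and stepwise selection, choose variables from the same data that then supply the odds ratios and intervals. When events are few, an effect tends to be kept only if its estimate happens to be large. The retained odds ratios are then biased away from 1, and ordinary 95% intervals take no account of the selection. Such estimates would feed the search for screening markers.

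The second issue is the population. A model with tobacco, alcohol or sexual history can use only patients who received the questionnaire. In a stepwise sequence, the fitted population can change when such a variable enters. The result describes adolescents and adults from about 16, in a study that enrols from age 0 to 65, and section 12 does not say so.

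**Working it through.** **Inputs from the protocol.** Table 6 strata; 2% to 8% baseline tonsil prevalence (section 12.4); 6.5% for oral HPV and 31% for scrapes and washings (section 12.3); tonsil studies in Table 2.

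**Cohort total.** 5 × 150 + 100 + 60 + 15 = 925, which reproduces the planned enrolment.

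**Patients without a questionnaire.** Aged 14 or under: 3 × 150 = 450 (48.6%). Assuming uniform ages within 15–19, one fifth of that stratum is aged 15: 150/5 = 30.
- Limit at 16 or over: 450 + 30 = 480 without (480/925 = 51.9%), 445 with.
- Limit above 16: 450 + 60 = 510 without (55.1%), 415 with.

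**Pooled Table 2 rate.** (2 + 0 + 3 + 1 + 5 + 6 + 13 + 0 + 0) / (195 + 226 + 69 + 50 + 64 + 106 + 206 + 48 + 14) = 30/978 = 3.1%.

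**Expected events** = patients × prevalence, with prevalence taken as equal at all ages:

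| Prevalence | 925 patients | 445 patients |
|---|---|---|
| 2% | 18.5 | 8.9 |
| 3.1% (Table 2 pooled) | 28.4 | 13.7 |
| 6.5% | 60.1 | 28.9 |
| 8% | 74.0 | 35.6 |
| 31% (scrapes and washings) | 286.8 | 137.9 |

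At a rule of thumb of ten events per parameter, 2% to 8% supports 1.9 to 7.4 parameters in the full cohort and 0.9 to 3.6 in the subset. The current-cohort values in Table 7 (4.1% to 11.6%) are detectable alternatives, not forecasts; they would give 38 to 107 events in 925 and 18 to 52 in 445.

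**Illustration 1: one exposure, reported only when p < 0.05.** Assumed: 40% exposed, true OR 1.5, 20,000 runs. Geometric mean OR given significance:

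| Prevalence | 445 patients | 925 patients |
|---|---|---|
| 3.1% | 4.1 | 2.6 |
| 6.5% | 2.7 | 2.0 |
| 31% | 1.8 | 1.6 |

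**Illustration 2: backward stepwise at p < 0.05.** Assumed: ten binary candidates, 30% exposed, one true OR of 2.0, 400 runs:

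| Patients, events | Median OR when selected | Median OR, full model without selection |
|---|---|---|
| 925, 18 | 3.39 | 1.98 |
| 925, 60 | 2.18 | 2.01 |
| 925, 287 | 2.01 | 2.03 |
| 445, 9 | 5.40 | 2.08 |
| 445, 29 | 2.71 | 2.03 |
| 445, 36 | 2.53 | 1.96 |
| 445, 138 | 2.07 | 2.04 |

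Keeping an odds ratio only when it is significant causes the exaggeration. It is large at 9 to 18 events, moderate at about 30, and negligible above about 140 for this effect size. Estimates from the unselected model centre on the true value throughout.

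**The case against.** The strongest reply is that section 12.2 defers detail to the SAP, and that the selection sentence lists alternatives, one of which is causal reasoning. A SAP with a causally chosen list would comply. That stands in part: stepwise selection is permitted, not required. But the protocol positively endorses data-driven routes, so this is a method stated badly and not one left open.

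Four stronger readings are tempting and not supported:

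- **That the odds ratios will be inflated.** This depends on the route taken and on the outcome. Section 12.3 reports that "in an analysis of oropharyngeal scrapes and oral washings, the prevalence of HPV detection was much higher at 31" per cent. At that level the oropharynx model would have ample events and little distortion.
- **That half the cohort would drop out silently, or that results would be labelled as the whole cohort.** The age limit is stated openly, and the protocol does not say how missing covariates are handled. Models limited to age, gender, vaccination and serology keep all ages.
- **That stepwise selection is what creates false risk factors.** With ten null candidates (40% exposed) in 445 patients, a fixed model without selection gave at least one p < 0.05 in 29% of runs at 3.1% prevalence and 38% at 6.5%; the first forward step alone gave 26% and 37%. Ten independent tests would give 1 − 0.95^10 = 40%. This is multiplicity, and it would affect a pre-specified list of ten as well.
- **That the models face 14 to 60 events.** The 14 belongs to the 445 patients at 3.1% and the 60 to the 925 at 6.5%; they are not one range.

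Two further points stand. The protocol gives no number of candidates, exposure rate or effect size, so the simulations only illustrate. And no listed objective asks for risk-factor odds ratios; the primary prevalence estimate and the historical comparison do not depend on them.

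**Conclusion.** The point holds as a defect in a secondary analysis that is cheap to correct. The protocol permits selection from the data without regard to the number of events. It also names variables that about 52% of the planned cohort will not have (55% under the section 7 wording), without declaring the resulting population.

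For the tonsil outcome, about 9 to 36 events are expected in the questionnaire group and about 18 to 74 in the full cohort. At these counts, odds ratios retained for significance could be materially too large and their intervals too narrow. For the oropharynx outcome near 31%, the effect is small.

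The subset counts rest on uniform ages within 15–19 and equal prevalence by age. Section 12.3 treats those aged 14 and under as non-exposed, so the older group may hold more events. In the extreme it holds all 18.5 to 74, which is still few for a long candidate list. The size of the exaggeration depends on the assumed effect: at 60 events in 925 it is about 9% for a true OR of 2.0 (2.18/2.0) and about 33% for 1.5 (2.0/1.5).

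**What to change.** In section 12.2.2, delete the descriptive-statistics and stepwise routes. Pre-specify, on causal grounds, a short covariate list sized to the expected events:

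1. **All ages:** age, gender, vaccination status and one named serological marker, with centre added if events allow.
2. **Aged 16 and over, declared as such:** the same terms plus two or three named questionnaire exposures.

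Use penalised (for example Firth) logistic regression when events are few. At the low end of the prevalence range even these lists exceed ten events per parameter's allowance, so state in advance which terms are dropped first. Report patients and events for each model, and label the second as applying to that age group only. Give one age limit for the questionnaire in both the Study Summary and section 7.

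The cost is wording only. The downside is that fewer variables are adjusted for; the rest can be shown unadjusted and labelled exploratory.
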